3.1 General Design

This is a 12-week, prospective, randomized clinical trial of the moderating effect of rs2832407 on the efficacy of topiramate in reducing HD in 200 individuals of European descent with DSM-5

CONFIDENTIAL

This material is the property of the University of Pennsylvania. Do not disclose or use except as authorized in writing by the study sponsor

AUD. We will stratify the randomization on genotype and oversample rs2832407*C homozygotes, the most topiramate-responsive genotype, to ensure comparable numbers of subjects in the four medication x genotype groups. We will compare the efficacy of topiramate to placebo in reducing the frequency of HDDs in subjects with AUD using a two-arm, parallel-groups design. Subjects will either have a goal to reduce their drinking to safe levels or to stop drinking entirely. We will use daily data collection to examine changes in relevant process variables and their interaction with genotype and medication group as predictors of HD. This study will be registered on clinicaltrials.gov.

At each visit, all subjects will receive MM (Pettinati, Weiss et al. 2004) (see section 6.7.2), which was developed for the COMBINE Trial and which we modified to be relevant for both reducing heavy drinking and promoting abstinence. Random assignment to treatment group and double-blind conditions will be maintained throughout the study. Raters will be trained in the reliable use of all assessments. We will use serum GGTP and percent disialotransferrin (%dCDT), an improved assay for carbohydrate deficient transferrin (Helander, Wielders et al. 2010), to validate subject reports. Following a one-week pre-treatment assessment period, subjects will receive 12 weeks of treatment. There will be a 6-day taper period, during which subjects will reduce their dosage of topiramate gradually and then discontinue it completely. Daily reports during the treatment period will be obtained using interactive voice response (IVR) to identify subjective correlates of medication effects and to monitor medication use. Following the 12-week treatment period, subjects will be asked to return to the clinic for 3-month and 6-month post-treatment follow-up visits to evaluate the durability of treatment effects.

3.2 Primary Study Endpoints

3.2.1 To examine the moderating effects of the GRIK1 SNP rs2832407 on the response to topiramate: The primary outcome measure will be the frequency of HDDs (≥ 5 standard drinks in a day for men and ≥ 4 in a day for women). We chose this outcome because it is a sensitive, clinically relevant measure in alcohol treatment trials (Falk, Wang et al. 2010). Subjects will be followed irrespective of whether they continue to receive treatment, so that the analysis of all outcomes will be based on all of the data available for all randomized subjects. Drinking data for this aim will come from the TLFB (see section 6.10 below).

3.2.2 To examine the relations among daily process measures, medication use, and drinking level: We will use multilevel models to evaluate the associations of alcohol expectancies and self-efficacy (confidence in resisting drinking and heavy drinking) with daily drinking and how these associations vary as a function of medication group and rs2832407 genotype. Similar to Kranzler, Armeli et al. (2013), we will focus on predicting nighttime drinking (i.e., drinks consumed after the early evening report), but here we will use alcohol-related expectancies reported during the early evening in the daily survey. Nighttime drinking levels will be determined by subtracting the number of drinks consumed during the current day from the total number of drinks consumed for that day (reported the following day).

3.3 Secondary Study Endpoints

Secondary endpoints include: the number of abstinent days, absence of any heavy drinking days [the FDA-recommended outcome measure ([name], Litten et al. 2012)], mean daily alcohol consumption, drinks/drinking day, %dCDT and GGTP levels, and severity of alcohol-related problems (i.e., SIP score), using models similar to those described below for the primary outcome. All outcomes (primary and secondary) will also be evaluated at 3- and 6-month post-treatment assessments.

3.4 Primary Safety Endpoints

Subjects will be monitored carefully for adverse events including the development of renal calculi or metabolic acidosis. At each study visit, participants will provide subjective reports of side effects using the adverse events checklist developed from prior studies of topiramate for alcohol treatment. Using data from that periodic inquiry, we will compare the medication groups on the overall frequency of adverse events during treatment, the frequency of severe adverse events during treatment, and the frequency of adverse events during treatment that are rated moderate or severe.

4 Subject Selection and Withdrawal

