Other adverse effects (experienced by 5-9% of subjects) in some clinical trials include: nervousness, slow thinking, abnormal vision, confusion, decreased sensitivity (hypesthesia), anxiety, abdominal pain, dry mouth, involuntary muscle contractions, and language problems. Depression and mood problems have also been reported (experienced by 5-9% of subjects). Some individuals have had suicidal thoughts or actions (experienced by about 1% of subjects). Although these adverse effects have not been reported in alcohol-dependent subjects, study participants will be informed that, should they feel a change in their mood, feel depressed, or feel they may harm themselves, they should contact the study doctor.

An adverse effect of topiramate, which is less common but potentially serious is renal calculi (experienced by about 2% of subjects). Drinking an adequate volume of fluids is recommended while taking topiramate, and may reduce the risk of renal calculi. Subjects will be counseled to drink water frequently throughout the day.

Severe metabolic acidosis (increased bicarbonate levels) is associated with topiramate treatment in 3-7% of individuals taking the medication. We will repeat bicarbonate levels at the visit six of the study to identify anyone with severe acidosis. Further, individuals taking carbonic anhydrase inhibitors will be excluded from this study, due to the added risk of metabolic acidosis. Treatment with topiramate may cause oligohidrosis (decreased sweating), which has primarily been reported in children.

Acute secondary glaucoma has been described in some people taking topiramate, usually occurring at the beginning of treatment (less than 1%). Individuals with a history of narrow angle glaucoma will be excluded from this study. Subjects will be informed that should they have sudden, significant worsening of vision, blurred vision, or eye pain to contact the study doctor immediately. This adverse event is very rare. Overdoses of topiramate have been associated with convulsions, drowsiness, speech disturbance, blurred vision, diplopia (double

CONFIDENTIAL

vision), impaired mental activity, abnormal coordination, stupor, hypotension, abdominal pain, agitation, dizziness and depression. Deaths have been reported in overdoses.

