Also, at the **week six visit**, the study staff will obtain a blood sample to measure bicarbonate levels, as topiramate can cause metabolic acidosis, and GGTP and %dCDT concentrations to corroborate self-reported alcohol consumption. At visits 5 (week 5) and 7 (week 8), study staff will obtain a urine sample for a pregnancy test for subjects who are women of childbearing potential. If a subject reports being pregnant or tests positive, she will immediately be withdrawn from treatment with study medication, referred for obstetric evaluation, and advised to discontinue all drinking.

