These assessments serve to: 1) screen subjects for medical exclusion criteria, 2) assess potential adverse effects of topiramate, and 3) corroborate self-reported drinking. Prior to entrance into the study, each subject will receive a physical exam, urinalysis and urine toxicology, CBC, a chemistry panel [which includes electrolytes, liver enzymes (ASAT, ALAT, GGTP), bilirubin, uric acid, BUN, and creatinine], %dCDT, and pregnancy testing for women of childbearing potential. Bicarbonate levels will be repeated at the week six visit because topiramate can cause metabolic acidosis. Pregnancy testing for women of childbearing potential will also be repeated at visits 1 (week 1), 5 (week 5), 7 (week 8), and 9 (week 11). If a subject reports being pregnant or tests positive, she will immediately be excluded or withdrawn from treatment with medication, referred for obstetric evaluation, and advised to discontinue all drinking. At the week six visit and endpoint, GGTP and %dCDT will be repeated to corroborate self-reported alcohol consumption. %dCDT will be measured in the laboratory of [name]

CONFIDENTIAL

[name], using the HPLC reference assay method, recommended for the measurement of %dCDT, the new standard analyte for measurement of CDT. This method corrects for total transferrin concentration and increases the utility of CDT to evaluate heavy drinking in women (Helander, Wielders et al. 2010).

6.11 Study Timeline:

Table 3: Timeline of Performance Goals

Activity	Year 1	Year 2	Year 3	Year 4	Year 5
Staff training & study preparation	■				
Subject enrollment	■	■	■	■	■
Endpoint assessments	■	■	■	■	■
Data entry & cleaning	■	■	■	■	■
Data analysis				■	■
Report writing				■	■

7 Statistical Plan

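### Every planned between-arm safety comparison uses the self-report checklist, so laboratory-detected acidosis and the Visit 6 bicarbonate have no prespecified by-arm result

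*Combined protocol and SAP*

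**What the plan says.** Section 3.4 opens with "Subjects will be monitored carefully for adverse events including the development of renal calculi or metabolic acidosis". Its data source follows: at each visit "participants will provide subjective reports of side effects using the adverse events checklist developed from prior studies of topiramate for alcohol treatment". The comparison is then defined: "Using data from that periodic inquiry, we will compare the medication groups on the overall frequency of adverse events during treatment". The same sentence adds two more comparisons, of severe events and of events rated moderate or severe, from the same source. Section 6.3 describes the checklist as nurse-administered and derived from completed topiramate studies. Its items are not given.

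Bicarbonate is measured at screening (section 6.2, Table 2) and once on treatment. Section 6.4 says that at the week six visit "the study staff will obtain a blood sample to measure bicarbonate levels, as topiramate can cause metabolic acidosis", and section 6.10 repeats this: "Bicarbonate levels will be repeated at the week six visit because topiramate can cause metabolic acidosis". Section 1.5 gives the purpose: "We will repeat bicarbonate levels at the visit six of the study to identify anyone with severe acidosis". It also gives the expected rate: "Severe metabolic acidosis (increased bicarbonate levels) is associated with topiramate treatment in 3-7% of individuals taking the medication".

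Section 7.2 covers the drinking aim and the daily-process aim only. Section 7.3 defines a safety population (randomized, at least one dose) but attaches no analysis to it.

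Outside the analysis plan, section 8.1 lists conditions under which an abnormal laboratory value is documented as an adverse event, and section 8.2 requires all adverse events to be recorded. Section 8.3.1 (Data and Safety Monitoring Plan) requires an annual adverse-event summary to both IRBs and NIAAA. Section 8.3.4 puts laboratory data within DSMB review.

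**The concern.** Two harms are singled out under the safety-endpoint heading, and one of them is identified by a blood test. The plan collects that test twice, then defines its between-arm comparisons on a different source. This is more than missing detail: the stated source leaves out events that sections 8.1 and 8.2 require to be recorded, unless they also reach the checklist.

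At stake is what the final safety results can say. If 3.4 is followed as written, the by-arm tables rest on subjective reports. They need contain no bicarbonate figure and no count of laboratory-detected acidosis, even though paired values exist in both arms. A missing by-arm result could be read as a null one. If the gap is filled after unblinding, the threshold, the population and the summary would all be chosen with the data in view.

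**Working it through.** The plan states no sample size, power or alpha for safety, so there is no figure to reproduce. The check has four parts.

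**1. Where each data source goes**

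| Source | Collected | Planned use |
|---|---|---|
| Adverse-event checklist | Visits (3.4, 6.3, Table 2) | Three by-arm comparisons (3.4) |
| GGTP, %dCDT | Screening, Visit 6, endpoint, follow-up (Table 2) | Secondary endpoints, modelled (3.3) |
| Bicarbonate | Screening, Visit 6 (6.2, 6.4, 6.10, Table 2) | Individual case-finding (1.5); no by-arm result |
| Laboratory abnormality meeting 8.1 | When found | Adverse-event record (8.2), annual summary (8.3.1), DSMB (8.3.4); no by-arm result in 3.4 or 7 |

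No bicarbonate threshold, change score or by-arm summary appears anywhere. GGTP and %dCDT are also drawn at Visit 6 and do have a planned analysis.

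**2. Size**

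Inputs: 3-7% on topiramate (1.5) and 100 per arm (5.3). My assumptions are two-sided alpha 0.05 and a placebo rate of 0% or 1%, since the documents give none.

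- Expected severe cases on topiramate: 100 × 0.03 = 3, up to 100 × 0.07 = 7.
- Chance of at least one: 1 − 0.97^100 = 95.2%, up to 1 − 0.93^100 = 99.9%.
- Fisher's exact test with no placebo cases: 5 against 0 gives p = 2 × C(100,5)/C(200,5) = 0.059, and 6 against 0 gives p = 2 × C(100,6)/C(200,6) = 0.029. Six cases are therefore needed, and power is P(X ≥ 6) for X ~ Binomial(100, p). The 1% column comes from full enumeration.

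| Topiramate rate | Power, placebo 0% | Power, placebo 1% |
|---|---|---|
| 3% | 8% | 3% |
| 5% | 38% | 19% |
| 7% | 71% | 44% |

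Some cases would very probably occur, but a test on the counts would usually miss the difference. Counts should be described, and the continuous value carries more information. With n values per arm, the 95% CI half-width for a baseline-adjusted mean difference is about 1.96 × √(2(1 − ρ²)/n) SD. At n = 100 this is 1.96 × √0.02 = 0.28 SD for ρ = 0, 0.28 × √0.75 = 0.24 SD for ρ = 0.5, and 0.28 × √0.51 = 0.20 SD for ρ = 0.7. The correlations are assumed. The documents give no bicarbonate SD, so these cannot be turned into laboratory units. They are also best cases: section 6.6 allows visits by phone, and the 94% in section 7.1 is an assumption about drinking data and does not give a rate of blood draws.

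**3. What the Visit 6 value represents**

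Table 1 dispenses 150 mg/day at Visit 5 and first dispenses 200 mg/day at Visit 6. The only on-treatment bicarbonate is drawn at Visit 6. Under the schedule it therefore reflects titration dosages, and no scheduled value falls in the 200 mg/day period.

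**4. Direction of change**

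Section 1.5 equates acidosis with increased bicarbonate (quoted above). The baseline laboratory list in section 6.2 says topiramate may lower it. A mean difference can be reported either way, but a count beyond a limit cannot be written until the two statements are reconciled.

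**The case against.** The strongest reply is that acidosis is covered elsewhere. Qualifying laboratory abnormalities are adverse events (8.1) and must be recorded (8.2). They enter an annual summary (8.3.1), and clinical test results are listed among the monitoring data. Section 8.3.4 has the DSMB review laboratory data precisely because they reflect differences between groups, and lets it ask for formal analyses. All of this stands. A reader might infer that the trial would not report acidosis at all, and the documents do not support that.

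A reader might also infer that acidosis is a defined endpoint left without analysis. That too goes further than the text. Section 3.4 gives acidosis as an example of a monitored event, and section 1.5 gives the repeat draw a case-finding purpose. Nor can anyone say the checklist would miss acidosis, since its items are not in the documents.

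What survives is narrower. The annual summary is not specified by arm. The DSMB receives safety data blinded by default, and its report to investigators on serious and unexpected events does not disclose arm (8.3.4). These routes protect individuals, but none commits the trial to a between-arm result. A final objection is that an analysis of the Visit 6 value could itself give false comfort because of its timing. That is fair, and it is a reason to state the limitation alongside the result.

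**Conclusion.** The point holds as a gap between the harms named in 3.4 and the data its comparisons admit. Laboratory-detected acidosis, and any renal calculus that does not reach the checklist, would be handled through adverse-event recording, annual summaries and DSMB review, outside the planned between-arm comparison. The bicarbonate values have no by-arm summary.

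The size is modest but real: 3 to 7 expected severe cases per 100 on topiramate. This applies the rate in section 1.5 as it stands. That rate is not tied to the dosages in force when the Visit 6 sample is taken, so the number found at that draw may differ. The power figures rest on the assumed placebo rates and alpha, and serve only to show that estimates suit these data better than a test on counts. The primary efficacy analysis is unaffected. The change should be made before unblinding.

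**What to change.** In sections 3.4 and 7:

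- Extend the by-arm adverse-event comparison, in the safety population, to events from any source (checklist, laboratory, clinical report). Count each event once if it arrives by more than one route.
- Tabulate acidosis events and renal-calculus events by arm, as number and percentage.
- Report Visit 6 bicarbonate by arm as a mean difference adjusted for the screening value, with a 95% CI, the number outside the laboratory's reference limit, and the number of values available per arm. Present these as estimates.
- State that under Table 1 the Visit 6 value precedes the 200 mg/day period and so cannot exclude acidosis at that dosage.
- Before writing any laboratory criterion, have the sponsor reconcile sections 1.5 and 6.2 on the direction of bicarbonate change.

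The cost is a few lines of plan wording, one extra table and one extra model. The values are already collected, so no new blood draw is needed.

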4.1 Inclusion Criteria

- 1) Determined to be physically healthy, based on medical history and physical examination and approval of the study physician
- 2) Age 18 to 70 years, inclusive
- 3) Self-identified European ancestry
- 4) Meets DSM-5 criteria for AUD
- 5) Average weekly ethanol consumption of ≥ 24 standard drinks for men and ≥ 18 standard drinks for women, with a weekly average of ≥ 2 HDDs during the month before screening
- 6) Stated goal to reduce drinking to safe levels or to stop drinking
- 7) Able to read English at an 8th grade or higher level and no gross cognitive impairment

CONFIDENTIAL

- 8) Willingness to nominate an individual who will know the subject's whereabouts to facilitate follow up during the study
- 9) Women of child-bearing potential (i.e., who have not had a hysterectomy, bilateral oophorectomy, tubal ligation or is less than two years postmenopausal): must be non-lactating and practicing a reliable method of birth control, and have a negative urine pregnancy test prior to the initiation of treatment. Examples of medically acceptable methods for this protocol include: the birth control pill, intrauterine device, injection of Depo-Provera, Norplant, contraceptive patch, contraceptive ring, double-barrier methods (such as condoms and diaphragm/spermicide), male partner sterilization, abstinence (and agreement to continue abstinence or to use an acceptable method of contraception, as listed above, should sexual activity commence), and tubal ligation.
- 10) Willingness to provide signed, informed consent and commit to completing the procedures in the study

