Rare and isolated cases of liver failure/hepatitis and blistering skin rashes (bullous skin eruptions) have been reported with topiramate (less than 1% for both). Careful instructions on the use of topiramate and dispensing of limited quantities of the medication will serve to reduce the risk of accidental overdose. Careful screening using module 2 of the MINI International Neuropsychiatric Interview 6.0 (MINI) will exclude individuals with significant suicidal risk and ongoing monitoring throughout the study will serve to reduce the risk of intentional overdose or other suicidal behavior. Suicidal risks will be assessed using the MINI Suicidality section (B) at each study visit, and if rated equal to or greater than 9 (i.e., clinically significant suicidal ideation), the physician will be consulted to decide the appropriate clinical management.

It is possible that some hormonal contraceptives (birth control pills, hormonal implants or hormonal injections) may be made less effective by topiramate. If appropriate, the study doctor will discuss alternatives or additional non-hormonal methods of birth control to be used during participation in the study. Women of childbearing potential who are using hormonal contraceptives will be instructed to inform the study nurse about any changes in menstrual bleeding patterns. Further, at the time of randomization, for women using hormonal contraceptives, the study physician will discuss with the participant non-hormonal methods of birth control to be used during her participation in the study.

Topiramate is labeled by the Food and Drug Administration as a category D medication. This means that there are data in humans from investigational or marketing experience showing that topiramate can cause harm to the fetus, but potential benefits may warrant the use of the medication in pregnant women despite risk to the potential risks. Data from pregnancy registries show that infants exposed to topiramate *in utero* have an increased risk for cleft lip and or cleft palate (oral clefts). Pregnancy testing of women of childbearing potential prior to study randomization (Screening and Informed Consent visit) and at visits 1 (week 1), 5 (week 5), 7 (week 8), and 9 (week 11) will minimize the risk of fetal exposure to study medication.

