the study in relation to efficacy. An adequate evaluation of efficacy will require a sample size larger than what will be available before the study is completed as designed. However, if it has been determined, for any reason, that the study should be suspended, we will discontinue enrollment of new patients, while continuing the treatment and monitoring of patients already enrolled in the study, unless to do so would create a risk that is not justified by any potential benefit to patients.

Women of Reproductive Age: As noted above, precautions for pregnant or reproductive age women are in accordance with NIAAA requirements and this will be monitored as part of the DSMP. Women who are pregnant, nursing or of reproductive age and not using effective methods of birth control will be excluded from the study. The study inclusion and exclusion criteria, in total and as specified in the protocol, will be the basis for determining study eligibility. As mentioned above, it is possible that some hormonal contraceptives (e.g., birth control pills, hormonal implants or hormonal injections) may be made less effective by topiramate. If appropriate, the study doctor will discuss with patients alternatives or additional non-hormonal methods of birth control to be used during participation in the study.

Data and Record Safety/Confidentiality: Records, filed in the IRB office, verify that all research project personnel have completed training in the protection of human research subjects in accordance with the guidelines of the U.S. Department of Health and Human Services (DHHS) and the Office for Human Research Protection (OHRP). The study staff (PI, clinical research coordinator, etc.) will keep all study medical records (including any codes to de-identified data) under lock and key in a secure location, as required by law. All electronic data and files (e.g., database, spreadsheet, etc.) containing identifiable patient information shall be password protected. Any computer hosting such files shall have a BIOS password to prevent access by unauthorized users. If patient data are to be exchanged with others, the data will be coded. If identification is necessary, then the data will be encrypted while en-route to the recipient with strong encryption levels (≥ 128 bits for symmetric encryption (DES) and ≥ 1024 bits for asymmetric encryption (RSA)).

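### Criterion 9 accepts the pill, Depo-Provera or Norplant as a sole method, although section 1.5 says topiramate may weaken such methods and raises oral-cleft risk; non-hormonal contraception is discussed but never required

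*Combined protocol and SAP*

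**What the plan says.** **Eligibility.** Criterion 9 (section 4.1) asks a woman of child-bearing potential for one reliable method and a negative urine pregnancy test before treatment. On which methods count, it says: "Examples of medically acceptable methods for this protocol include: the birth control pill, intrauterine device, injection of Depo-Provera, Norplant, contraceptive patch, contraceptive ring". Double-barrier methods, partner sterilization and abstinence follow as further items in the same list. They are alternatives, not additions to a hormonal method.

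**The interaction and the harm.** Section 1.5 says it is possible that "some hormonal contraceptives (birth control pills, hormonal implants or hormonal injections) may be made less effective by topiramate". It gives topiramate's pregnancy category as D and reports a raised risk of oral clefts after exposure in utero.

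**The safeguards.** For women on hormonal contraception, section 1.5 says that at randomization "the study physician will discuss with the participant non-hormonal methods of birth control to be used during her participation in the study". It also says: "Women of childbearing potential who are using hormonal contraceptives will be instructed to inform the study nurse about any changes in menstrual bleeding patterns". Pregnancy tests are scheduled at screening and at visits 1, 5, 7 and 9 (section 1.5, section 6.10 and Table 2). A woman found to be pregnant stops study medication.

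**The monitoring plan.** Section 8.3.1 says: "Women who are pregnant, nursing or of reproductive age and not using effective methods of birth control will be excluded from the study". The next sentence reads: "The study inclusion and exclusion criteria, in total and as specified in the protocol, will be the basis for determining study eligibility". The same paragraph repeats the interaction and adds: "If appropriate, the study doctor will discuss with patients alternatives or additional non-hormonal methods of birth control".

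**The concern.** The plan accepts, without back-up, three methods of the kinds that it says the study drug may weaken: the pill, the injection and the implant. Because the drug is also described as harmful to a fetus, one would expect the eligibility rule to carry the consequence. It does not. The consequence appears only as a conversation in the risk section.

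What is at stake is a woman who meets every criterion, hears the discussion, keeps her hormonal method alone and takes topiramate for up to 90 days. Nobody would have departed from the protocol. The harm at issue is serious and falls on a third party. The remedy uses methods that the plan already accepts.

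**Working it through.** **Does any safeguard make a non-hormonal method a condition?** No figure in the plan needs to be reproduced. The question is what each provision requires.

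| Provision | What it requires | Closes the gap? |
|---|---|---|
| Criterion 9 (4.1) | One acceptable method; pill, injection and implant qualify alone | No, this is the source |
| Discussion at randomization (1.5) | Unconditional for hormonal users, but only a discussion | No; adoption is not required or recorded, and dispensing does not depend on it |
| Discussion where appropriate (1.5, 8.3.1) | Left to the physician's judgement | No |
| Bleeding reports (1.5) | The woman tells the nurse; no resulting action is stated | No |
| Pregnancy tests (1.5, 6.10, Table 2) | Find a pregnancy after conception | No; they limit the length of exposure |
| Exclusion of women without effective methods (8.3.1) | Eligibility then refers back to the criteria | No; criterion 9 counts these hormonal methods as acceptable |
| Exclusion 12 (4.2) | General discretion over suitability | No; it does not mention contraception |

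For comparison, exclusions 4 and 11 in section 4.2 turn two other topiramate interactions (carbonic anhydrase inhibitors and dolutegravir) into eligibility rules.

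**How many women could be affected?** The documents give arms of 100 (section 5.3) and a female share of about 30% (section 4.3) or 32% (section 4.1.1).

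- Women on topiramate: 0.30 × 100 = 30 to 0.32 × 100 = 32.
- Women in both arms: 60 to 64.

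This is a ceiling. It includes women who are postmenopausal (the age limit is 70), sterilized or already using non-hormonal methods. The share relying on hormonal methods alone is not given. Assumed shares of 10%, 25% and 50% of 32 give about 3, 8 and 16 women.

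**How many pregnancies?** Time on drug is 84 + 6 = 90 days (sections 6.4.1 and 6.6). Annual failure rates p of 5% to 15% are assumed. The risk over 90 days is 1 − (1 − p)^(90/365):

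- p = 0.05: 0.0126
- p = 0.10: 0.0256
- p = 0.15: 0.0393

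Multiplying by the number of women gives the expected pregnancies from all causes. The excess is the part due to the interaction. It is shown for a rise in annual failure from 5% to 10% (0.0131 per woman, from unrounded risks) and, as a harsher case, from 5% to 15% (0.0393 − 0.0126 = 0.0267 per woman). Both rises are assumed.

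| Hormonal-only women on topiramate | All causes, p = 5% to 15% | Excess, 5% to 10% | Excess, 5% to 15% |
|---|---|---|---|
| 3 | 0.04 to 0.12 | 0.04 | 0.08 |
| 8 | 0.10 to 0.31 | 0.10 | 0.21 |
| 16 | 0.20 to 0.63 | 0.21 | 0.43 |

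Only the excess columns measure the gap. The all-causes column includes failures that would occur without any interaction.

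**The case against.** The strongest reply is that the plan already recognises the risk and handles it. The randomization discussion is owed to every hormonal user, and its wording looks ahead to non-hormonal methods being used during the study. Criterion 9's list gives examples under a standard of reliability. The study physician must approve entry and may refuse an unsuitable candidate. Section 8.3.1 states that the precautions accord with NIAAA requirements and will be monitored. Those requirements are not in the documents, and the consent pages were not available for review. Finally, section 1.5 speaks only of a possibility for some methods, and the size of the effect is assumed.

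Much of this stands. It would be wrong to infer that the plan ignores the interaction, or that many pregnancies should be expected. It remains true that the operative verb is *discuss*, and that the criteria which govern eligibility accept the hormonal method alone. Consent wording could add a duty for the participant, but it would not change criterion 9.

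A reader might also infer three further faults that the documents do not support.

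- *An affected birth would go unreported.* Section 8.1 lists a congenital anomaly or birth defect as a serious adverse event. Section 8.2 requires immediate reporting of a possibly related serious event after the study period. Section 8.1 also has participants told at the last visit to report later events.
- *A visit 10 pregnancy test is missing from Table 2.* The remark in section 6.5 is repeated text that also appears for visits 2 to 8, where only visits 5 and 7 are tested. Visit 10's own assessment list contains no such test.
- *Section 4.4.1 loses pregnant women to follow-up*, because it speaks of withdrawal from the study where sections 6.4 and 6.10 speak of withdrawal from medication. Section 4.4.2 invites withdrawn participants to all later visits, and section 3.2.1 follows participants whether or not they stay on treatment.

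**Conclusion.** The point holds on the text. The plan identifies a possible loss of contraceptive protection on a drug with fetal risk, requires a conversation about it, and stops short of requiring protection.

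Its size is small. At most 30 to 32 women on topiramate could be concerned, and probably far fewer. Under the assumed shares and failure rates, the excess is 0.04 to 0.21 pregnancies if failure doubles and 0.08 to 0.43 if it triples. Only some of these, a fraction not estimated here, would lead to a cleft. The hormonal-only share, the failure rates and the strength of the interaction are all assumptions.

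The change is worth making because the harm is severe and the remedy cheap, not because pregnancies are likely. The efficacy analysis is not in question. Section 1.5 does not name the patch or ring, so covering them is a precaution.

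**What to change.** 1. **Section 4.1, criterion 9.** Add that a woman of child-bearing potential using a hormonal pill, implant or injection (patch and ring as a precaution) must add, or switch to, a non-hormonal method already on the list, such as double-barrier. The requirement runs from first dose to the end of the taper and applies in both arms, which keeps the blind.
2. **Section 1.5.** Replace the duty to discuss with a duty on the study physician to confirm and record the non-hormonal method before study drug is dispensed.

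The cost is an amendment to the protocol, with matching consent wording if it is not already there, and one recorded item at randomization. At most 60 to 64 women across both arms would be asked. A few may be counselled, may switch method or may not be enrolled. Randomization, outcomes and analysis stay as they are.
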